4.1 DESIGN

Randomized, double-blind, placebo-controlled clinical trial, parallel design

- Intervention Arm: Hydroxychloroquine 800 mg orally once (4 tablets), followed in 6 to 8 hours by 600 mg (3 tablets), then 600 mg once a day for 4 consecutive days (5 days in total)
- Control Arm: Vitamin Placebo 4 tablets orally once, followed in 6 to 8 hours by 3 tablets, then 3 tablets once a day for 4 consecutive days (5 days in total)

4.2 Study participant duration

- 14 days consisting of internet-based virtual visits
- For participants ill with COVID-19 disease who are hospitalized (an SAE), observational follow up will extend to up to 90 days to assess final outcome status of their SAE.
- Pregnant women have their fetal outcome assessed postpartum to exclude a teratogenic SAE.

4.3 Study procedures

- All procedures will consist of internet-based questionnaires completed by self-report.
- Informed consent is provided to access medical records to verify information, as necessary.
- Optional: blood spot will be collected at approximately day 14.
- Optional: daily cardiac monitoring with remote EKG reads of QTc interval.

4.4 Individually identifiable health information:

Name, date of birth, addresses, and phone number will be collected so as to prescribe study medication. Email addresses will be collected for communication. If participants are hospitalized, the hospitalization date will be collected.

4.5 Substudies (if applicable)

Additional sub-studies will undergo separate IRB approval, and these studies will involve separate informed consent. Consented participants will be queried as to if they wish to participate in future research.

- 1) Serology for Coronavirus Antibodies: New Participants will be offer an optional participation in self-collection of dried blood spots in order to measure serologies for antibodies. Participants who have already been consented and entered the trial, will be approached for amendment of consent. The purpose of serology testing is two-fold: First, to verify infection. Second, the prevalence of antibodies will be compared among symptomatic and asymptomatic persons with a scientific question of how many asymptomatic persons seroconvert after a high risk exposure in the absence of symptomatic illness. The exact serology methodology to be conducted will be determined, based on availability and diagnostic performance. Blood spot collection materials (e.g. 18g lancet, filter paper, bandaid, instructions, and return envelope). (Optional)
- 2) Cardiac Monitoring with handheld EKG to check cardiac QTc interval once daily for the first 7 days as a safety substudy. (Optional)

5 STUDY ENROLLMENT AND WITHDRAWAL

Participants will undergo screening via internet-based forms. The screening and inclusion criteria will be based on self-report.

5.1 Subject Inclusion Criteria

- Exposure to a COVID19 case within ≤ 4 calendar days as either:
 - Occupational exposure (healthcare worker, first responder, etc.)
 - Household contact
- OR
- Symptomatic COVID-19 disease
 - Confirmed diagnosis with PCR+ SARS-CoV-2 within ≤ 4 days of symptom onset
 - OR
 - Individual with compatible symptoms with exposure to known PCR+ SARS-CoV-2 case within 14 days AND compatible symptoms of fever, cough, or shortness of breath (and no available /pending testing for the individual)*
- ≥ 18 years of age
- Provision of informed consent

5.2 Subject Exclusion Criteria

- Current Hospitalization
- Contraindication or allergy to hydroxychloroquine
- Retinal eye disease
- Concurrent malignancy requiring chemotherapy
- Known glucose-6 phosphate dehydrogenase (G-6-PD) deficiency
- Known chronic kidney disease, stage 4 or 5 or receiving dialysis
- Known Porphyria
- Weight < 50 kg
- Structural or ischemic heart disease
- Personal or Family history of prolonged QT
- Current use of: hydroxychloroquine, chloroquine, or cardiac medicines of: flecainide, Tambocor; amiodarone, Cordarone, Pacerone; digoxin or Digox, Digitek, Lanoxin; procainamide or Procan, Procanbid, propafenone, Rythmal; or sotalol.
- Current use of QT prolonging medicines of:
 - Antimicrobials: levofloxacin, ciprofloxacin, moxifloxacin, azithromycin, clarithromycin, erythromycin, ketoconazole, itraconazole, or mefloquine
 - Antidepressants: amitriptyline, citalopram, desipramine, escitalopram, imipramine, doxepin, fluoxetine, wellbutrin, or venlafaxine
 - Antipsychotic or mood stabilizers: haloperidol, droperidol, lithium, quetiapine, thioridazine, ziprasidone
 - Methadone
 - Sumatriptan, zolmitriptan

Rationale for inclusion / exclusion criteria:

* As of 20 March 2020, testing is limited in many U.S. states and locales due to insufficient supplies. Thus, outpatient testing may not be available. A person with known exposure to a confirmed COVID-19 case with subsequent compatible symptoms is eligible for enrollment, if testing is not available. If a symptomatic person tests negative for SARS-CoV-2, they are not eligible for enrollment.

Mean Incubation period is ~5.2 days, thus we wish to limit enrollment to those with a higher risk of progression and deliver study medicine in a time period to intervene to prevent disease or ameliorate disease (i.e. start of study medicine by ≤ 4 days after exposure). The current (as of March 17, 2020) delays in testing makes this window particularly tight, and it may need to be relaxed in the future via protocol amendment.

In clinical practice of tropical medicine, chloroquine or hydroxychloroquine are prescribed without any baseline laboratory testing or monitoring.

Chronic use of hydroxychloroquine for >1 year can cause retinopathy or cardiomyopathy, thus persons with baseline conditions will be excluded. Study medicine is excreted via the kidney with dose reduction recommended in CrCl <30 cc/min (Stage 4 Kidney Disease). G-6-PD deficiency is listed as a caution on the FDA label. G-6-PD testing is not routinely performed in clinical care prior to giving hydroxychloroquine prescriptions (unlike with primaquine). Medication exclusions are for possible drug-drug interactions, particularly with cardiac arrhythmia medicines with a caution on the FDA-package insert.

On April 20, 2020, FDA mandated exclusion of structural or ischemic heart disease; or personal or family history of prolonged QT.

On April 24, 2020, FDA issued a caution for QT prolongation in persons with heart disease, chronic kidney disease, or taking other QT prolonging medicines.

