Primary Endpoint in Asymptomatic Cohort	
 ● Incidence of COVID-19 disease within 14 days among those who are asymptomatic with known exposure
Primary Endpoint in Symptomatic Cohort	
 ● Change in symptom severity score (visual analog scale 0-10) over 14 days
Secondary Endpoints	
 1. Incidence of Hospitalization for COVID-19 or death 2. Incidence of confirmed SARS-CoV-2 detection 3. Incidence of possible COVID-19 symptoms 4. Incidence of all-cause study medicine discontinuation 5. Severity of symptoms at Day 5 and 14 by visual analog scale 6. Ordinal Scale of COVID-19 disease maximum severity at day 14 among those who are symptomatic at trial entry
Duration of Participation	
Recruitment and follow up will be internet-based.
 
 ● 14 days of active participation ● Up to 90 days follow up for those with COVID-19 diagnosis to assess final outcome or dried blood spot collection for antibody serologies.
Inclusion Criteria	
 ● Exposure to COVID-19 within 4 days, either as: 
 ○ Occupational exposure, or ○ Household contact. 
OR
 
 ● Individual with symptomatic COVID-19 disease confirmed by PCR+ or by compatible symptoms with exposure to known PCR+ case with <=4 days of symptoms. ● Age >=18 years of age ● Provision of Informed Consent
Exclusion Criteria	
 ● Current hospitalization ● Allergy to chloroquine or hydroxychloroquine ● Prior retinal eye disease ● Concurrent malignancy requiring chemotherapy ● Known Chronic Kidney disease, Stage 4 or 5 or dialysis.

	
 • Known glucose-6 phosphate dehydrogenase (G6PD) deficiency. • Known Porphyria • Weight <50 kg • Structural or ischemic heart disease • Personal or family history of QT prolongation • Current use of: hydroxychloroquine, chloroquine, mefloquine, or cardiac medicines of: amiodarone, digoxin, dofetilide, flecainide, procainamide, propafenone, or sotalol • Current use of QT prolonging medicines, including azithromycin (Refer to protocol for full list).

Stratification
	
Randomization will be stratified by baseline status of COVID-19 disease vs. asymptomatic with exposure. Analyses will be separate for asymptomatic vs. symptomatic cohorts

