FDA cautions against use of hydroxychloroquine or chloroquine for COVID-19 outside of the hospital setting or a clinical trial due to risk of heart rhythm problems

Close supervision is strongly recommended

“The FDA is aware of reports of serious heart rhythm problems in patients with COVID-19 treated with hydroxychloroquine or chloroquine, often in combination with azithromycin and other QT prolonging medicines. We are also aware of increased use of these medicines through outpatient prescriptions. Therefore, we would like to remind health care professionals and patients of the known risks associated with both hydroxychloroquine and chloroquine. We will continue to investigate risks associated with the use of hydroxychloroquine and chloroquine for COVID-19 and communicate publicly when we have more information.”

“Hydroxychloroquine and chloroquine can cause abnormal heart rhythms such as QT interval prolongation and a dangerously rapid heart rate called ventricular tachycardia. These risks may increase when these medicines are combined with other medicines known to prolong the QT interval, including the antibiotic azithromycin, which is also being used in some COVID-19 patients without FDA approval for this condition. Patients who also have other health issues such as heart and kidney disease are likely to be at increased risk of these heart problems when receiving these medicines.”

Mitigation of Risk: The inclusion / exclusion criteria exclude cardiac risk factors, chronic kidney disease, and anti-arrhythmia medicines. On 24 April, additional QT prolonging medicines are excluded.

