6.2 Dosage, Preparation, and Administration of Investigational Product

Drug/Device Handling:

Hydroxychloroquine or placebo will be dispensed by the MHealth Investigational Drug Service (IDS) Pharmacy. To do so, study investigators will send a prescription to the IDS Pharmacy, the pharmacy will randomize the subject, and dispense the appropriate study medicine. The medicine will then be provided to research volunteers via FedEx / courier delivery in the United States.

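### Section 5.2 leaves dofetilide off both of its medication exclusion lists, although the protocol Summary excludes current users of it

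*Combined protocol and SAP*

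**What the plan says.** The exclusion criteria appear twice in the protocol.

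- **Summary, Exclusion Criteria.** One bullet excludes current users of hydroxychloroquine, chloroquine, mefloquine and "cardiac medicines of: amiodarone, digoxin, dofetilide, flecainide, procainamide, propafenone, or sotalol". The next bullet deals with QT-prolonging drugs by example and sends the reader elsewhere for the rest: "Current use of QT prolonging medicines, including azithromycin (Refer to protocol for full list".
- **Section 5.2, Subject Exclusion Criteria.** The corresponding bullet excludes hydroxychloroquine, chloroquine and "cardiac medicines of: flecainide, Tambocor; amiodarone, Cordarone, Pacerone; digoxin or Digox, Digitek, Lanoxin; procainamide or Procan, Procanbid, propafenone, Rythmal; or sotalol". A second bullet names QT-prolonging medicines under antimicrobials, antidepressants, antipsychotics or mood stabilizers, methadone and two triptans.

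Two other places state what the exclusions are for. Section 2.3.1, under Mitigation of Risk and directly after the FDA caution of 24 April 2020, says: "The inclusion / exclusion criteria exclude cardiac risk factors, chronic kidney disease, and anti-arrhythmia medicines". The rationale that follows the Section 5.2 list says: "Medication exclusions are for possible drug-drug interactions, particularly with cardiac arrhythmia medicines with a caution on the FDA-package insert".

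**The concern.** A summary may be shorter than the section it summarizes. Here the section is shorter than the summary, and on a safety exclusion. A reader who follows the Summary's pointer for the full QT list arrives at Section 5.2, where dofetilide does not appear. The protocol gives no rule on which text prevails, so eligibility on medication grounds depends on which page is used.

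Participant safety is what is at stake. Section 5 states that "The screening and inclusion criteria will be based on self-report", and Section 7.1 places this on a web form. Study medicine then goes out by courier. Section 6.2 does put a clinician's step in between ("study investigators will send a prescription to the IDS Pharmacy"), but no review of current medicines is described there. Handheld ECG monitoring is optional (Sections 4.3 and 4.5). With so little else in the path, the named-drug list is the main control on interacting medicines. If the form was built from Section 5.2, a dofetilide user not caught by another criterion could be randomized and sent hydroxychloroquine.

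**Working it through.** No formula applies; the check is a drug-by-drug comparison of the two lists. Brand-name synonyms of a drug already listed are not counted separately.

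**Step 1. Drugs in the Summary's current-use bullet.** Three antimalarials (hydroxychloroquine, chloroquine, mefloquine) plus seven cardiac medicines: 3 + 7 = 10.

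**Step 2. Drugs named in Section 5.2.**

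| Group in Section 5.2 | Number | Dofetilide named? |
|---|---|---|
| Hydroxychloroquine, chloroquine | 2 | No |
| Cardiac medicines | 6 | No |
| QT list: antimicrobials | 9 | No |
| QT list: antidepressants | 9 | No |
| QT list: antipsychotics or mood stabilizers | 6 | No |
| QT list: methadone | 1 | No |
| QT list: triptans | 2 | No |

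The QT list totals 9 + 9 + 6 + 1 + 2 = 27, and the two bullets together name 2 + 6 + 27 = 35 drugs.

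**Step 3. Match the Summary's ten against Section 5.2.**

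| Drug in the Summary | Where it is in Section 5.2 |
|---|---|
| Hydroxychloroquine | Current-use bullet |
| Chloroquine | Current-use bullet |
| Mefloquine | Moved to the QT list, antimicrobials |
| Amiodarone | Cardiac list |
| Digoxin | Cardiac list |
| **Dofetilide** | **Absent** |
| Flecainide | Cardiac list |
| Procainamide | Cardiac list |
| Propafenone | Cardiac list |
| Sotalol | Cardiac list |

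Nine of ten match, and six of the seven cardiac medicines. Dofetilide is the only one that does not.

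**Step 4. Could wording elsewhere in Section 5.2 bring it in?** Both bullets introduce a fixed enumeration, with no phrase covering similar drugs or a drug class. The nearest criteria are contraindication to hydroxychloroquine, structural or ischemic heart disease, personal or family history of prolonged QT, and stage 4 or 5 kidney disease or dialysis. Each would exclude some dofetilide users for another reason. None excludes a person because of taking the drug.

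**Step 5. Is the gap an artefact or a deliberate change?** The cardiac list in Section 5.2 reads as one complete sentence, with no redaction or broken table. Both texts are current criteria. Nothing in the documents explains a removal, and Section 2.3.1 says the medication exclusions were widened on 24 April.

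**The case against.** The best reply is that this is an omission and not a contested rule. Section 5.2 never says dofetilide users may enroll. The Summary is current protocol text and excludes them, and Section 2.3.1 says anti-arrhythmia medicines are excluded. Read together, two places point to exclusion and one is silent, so a careful investigator applying both lists would reach the right answer. That is fair as to intent. It does not help someone working from Section 5.2 alone, which is where one expects to find the complete criteria.

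Three further points have some force:

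- **The screening form is not in the documents.** If it followed the Summary, nobody was wrongly enrolled. The inconsistency in the text is established; an enrollment error is not.
- **Other safeguards narrow the exposed group.** These are the cardiac, QT-history, contraindication and kidney criteria, and the investigator's prescription. Section 6.6 also has participants report other therapies on day 1, but by then the study medicine has been delivered and dosing begins that day, so it might reveal a user without preventing exposure.
- **The rationale after Section 5.2 is qualified.** It refers to arrhythmia medicines that carry a caution in the package insert. The insert is not supplied, so that sentence does not show by itself that dofetilide was meant. The argument rests on the Summary, which names the drug, and on the statement in Section 2.3.1.

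These points limit the consequence. They do not remove the discrepancy.

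**Conclusion.** The concern holds. The Summary excludes current dofetilide use, and Section 5.2 does not name the drug in either of its medication lists. The discrepancy is one drug, with the other nine in the Summary's bullet accounted for. It should be corrected because it concerns a safety exclusion in a remote trial with self-reported eligibility and optional ECGs. It does not rank higher than that: the intent is clear, and sample size, power, alpha and the analyses are untouched.

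Two things cannot be settled from the documents: how many candidates take dofetilide, and which list the web form used. Any actual exposure depends on the form having followed Section 5.2 and on the person not being caught by another criterion. The conclusion that the two texts disagree depends on neither.

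**What to change.** Add dofetilide to the cardiac-medicine exclusion in Section 5.2, so that the seven cardiac drugs match the Summary. Confirm that the web screening form asks about it. The Summary can keep its abbreviated reference to the QT list.

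The cost is one word in the protocol and one check of the form. Sample size, randomization, blinding and analysis are unaffected.

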5.3 Treatment Assignment Procedures

5.3.1 Randomization Procedures

Participants will be randomized via permuted block randomization. Randomization will be recorded on an electronic log by the pharmacy. Study investigators and subjects will be blinded. There will be separate randomization schedules for the two cohorts (asymptomatic with exposure or symptomatic).

Masking Procedures

Participants will be provided masked study medicine, shipped by courier (e.g. FedEx). The intervention vs. placebo will not be identical; however, participants and outcome assessors will be masked to their assignment.

5.3.2 Reasons for Withdrawal

Participants may withdraw at any time point at their discretion.

5.3.3 Handling of Withdrawals

Withdrawals will be counted as failures for the secondary endpoint of completion of study medication.

Participants who discontinue study medication will still be asked to complete the follow up visit schedule.

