3.2.2 Secondary Outcome Measures

- Incidence of hospitalization or death
- Incidence of confirmed SARS-CoV-2 detection
- Incidence of symptoms compatible with COVID-19 (possible disease)
- Incidence of all-cause study medicine discontinuation or withdrawal
- Incidence of adverse reactions
- Symptom severity on day 5 or 14 via visual analog scale
- Ordinal Scale of COVID-19 Disease Severity at day 14 (among those who are symptomatic at trial entry)
 - Illness without hospitalization
 - Hospitalization (or post-hospital discharge)
 - Hospitalization with ICU stay or Death

Assessment of outcome measures will be primarily by self-report. As necessary, COVID19 disease will be verified from public health records, medical records, or death certificates. The primary endpoints are different for the two cohorts (those who are asymptomatic with known exposure; or those who are symptomatic at trial entry), and analyses will be done separately for the two cohorts.

The primary analysis will use PCR+ confirmed disease. However if the absence of sufficient testing supplies continues then outpatients will not be offered SARS-CoV-2 testing unless they are sick enough to be hospitalized. In that case an alternate a priori planned analysis will define incident COVID19 disease as a composite of SARS-CoV-2 PCR+ confirmed result OR symptomatic disease (i.e. possible) COVID-19 in those without testing.

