7 STUDY SCHEDULE

Screening Online Questionnaire

- Email [contact] or go to www.covidpep.umn.edu if you have been exposed to or diagnosed with COVID19
- You will be sent an email with information about our clinical trial
- A URL link will be provided for you to take the online screening survey

Medication Shipped

- Study medicine will be shipped overnight to your address
- Study medicine should arrive by 10:30am (Mon-Sat)
 - If you enroll after ~12pm on Sat or Sun, will arrive Tue.
- Take 4 tablets of the study medicine with some food or milk

Online Survey (Day 1)

- You will receive an email with a link to an online survey from [contact]. If not received, check your spam folder.
- Take the second dose of 3 tablets 6-8 hours after the first.
- Take other medicines \geq 4 hours apart from the study medicine

Study Days 2-4

- You should take 3 tablets each morning
- If you develop upset stomach, you may separate the pills; for example 1 at breakfast, 1 at lunch, and 1 at dinner.
- We will send a brief Day 3 survey

Online Survey (Day 5)

- You will receive an email with a link to an online survey
- This should be the same day you finish the study medicine
- A brief follow up survey will also be sent on Day 10 to ask if you have any COVID19 symptoms

End of Study Survey (Day 14)

- You will receive an email with a link to an online survey
- Unless you have developed symptoms, this marks the end of the study. We will ask if you wish to participate in future studies.
- If you were hospitalized or have pending tests, we will reach out to you every 2 weeks.

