7.3 Follow-up

Day 1 Virtual visit

- Verify receipt of study medicine
- Clinical status check-in
 - Participant starts study medicine (4 tabs), then 3 tabs in 6-8 hours, then 3 tabs daily.
- Query for SARS-CoV-2 testing
- Query for symptom status (0-10 visual analog scale of symptom severity)
- Query for hospitalization or SAEs
- Query for medication-related side effects / AEs

Day 3 Virtual visit

- Query for symptom status (0-10 visual analog scale of symptom severity)
- Query for hospitalization or SAEs
- Query for medication-related side effects / AEs

Day 5 Virtual visit

- Query for symptom status (0-10 visual analog scale of symptom severity)
- Assessment of adherence by self-report
- Completion of study medicine, which has a ~7 day half-life
- Query for study medicine side effects since enrollment
- Query for SARS-CoV-2 testing
- Query for hospitalization or SAEs

Day 10 Virtual visit

- Query for symptom status (0-10 visual analog scale of symptom severity)
- Query for SARS-CoV-2 testing

- Query for SARS-CoV-2 testing
- Query for hospitalization or SAEs

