- d. The primary outcome will be presented by subgroups formed by COVID test results (confirmed positive vs. other), age groups (18-35, 36-50, > 50), sex, and days from exposure onset to entry. These are apriori subgroups defined in the Version 1.0 of the protocol.
- e. Medication adherence is captured on study day 5. Another subgroup of interest is comparing the treatment groups for change in symptom severity score after day 5 by adherence reported at day 5 ($\leq 75\%$ versus $> 75\%$).

II. Secondary outcomes

- a. Secondary outcomes for incidence will be presented as proportions and compared between the treatment groups with Fisher’s Exact tests.
- b. Symptom severity scores were recorded with the online participant surveys at days 3, 5, 10 and 14 only for those who responded “yes” to “Any symptoms experienced”.

- i. Visual analog scale (0-10) for “overall symptom severity” is collected via a digital slider bar, which is marked with “0 = no symptoms”; 5 (placed in the middle); and “10 = severe symptoms”

Severity of overall symptoms?

Please click to move the slider, even if your symptoms are a 5

* must provide value

0 = No symptoms 5 10 = Most severe

- ii. For those who responded “no” to “Any symptoms experienced” the symptom severity score for that visit is assigned as zero.
- iii. For those hospitalized or with deaths, their symptom severity was scored as 10 if they did not respond to the visit survey.
- iv. Analysis is by Kruskal Wallis tests among those with symptoms at day 14.

Clarifications (24 May 2020):

- Participants with missing outcome data are still included in the denominator, as the trial is performed as an intent to treat analysis.
- Sensitivity analyses were performed excluding participants with missing data from the denominator as well as including participants with missing data as events.

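### Withdrawals count as failure to complete study medicine with no Day 5 cut-off, so participants who finish the course and leave later are misclassified

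*Combined protocol and SAP*

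**What the plan says.** Protocol 5.3.3 gives the scoring rule: "Withdrawals will be counted as failures for the secondary endpoint of completion of study medication". No time limit is attached. Section 5.3.2 adds: "Participants may withdraw at any time point at their discretion".

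The dosing period is short. Section 7 says of the Day 5 survey: "This should be the same day you finish the study medicine". Section 7.3 lists at the Day 5 visit: "Completion of study medicine, which has a ~7 day half-life". Section 6.5 takes adherence from self-report at that same visit. Section 4.2 sets 14 days of follow-up.

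Section 5.3.3 itself separates stopping the drug from leaving the study: "Participants who discontinue study medication will still be asked to complete the follow up visit schedule".

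The endpoint is worded in three ways:
- Summary, secondary endpoints: "Incidence of all-cause study medicine discontinuation"
- Section 3.2.2: "Incidence of all-cause study medicine discontinuation or withdrawal"
- Section 5.3.3: completion of study medication

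SAP part II compares secondary incidence outcomes as proportions with Fisher's exact test and says nothing specific about this endpoint. The SAP Clarifications of 24 May 2020 state: "Participants with missing outcome data are still included in the denominator". They then list two sensitivity analyses: one removes participants with missing data from the denominator, the other counts them as events.

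**The concern.** Whether someone finished the tablets is settled by Day 5. A withdrawal on Day 8 says nothing about it, yet the rule in 5.3.3 overrides the Day 5 report and scores that person as a failure. The three wordings count different people, and the SAP does not choose among them.

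At stake is the reading of a secondary endpoint that bears on how well the drug was tolerated. If similar numbers withdraw in both arms, the added failures dilute a real difference in stopping. If more withdraw in one arm, part of any difference would reflect leaving the study and not stopping the drug. Section 9.2.1 says that adverse events are not captured unless they lead to hospitalization, although 7.3 and 7.4 query side effects. That gives a clean discontinuation figure some extra value.

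**Working it through.** **No figure to reproduce.** The documents give no expected rate, power or sample size for this endpoint. The check therefore sets out how the wordings classify participants and then illustrates the size.

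**Course length.** From 4.1: 4 + 3 + (3 × 4) = 19 tablets over 5 days.

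**Classification under each wording**

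| Participant | Summary | 3.2.2 | 5.3.3 |
|---|---|---|---|
| Takes all 19 tablets, stays to Day 14 | no event | no event | completed |
| Takes all 19 tablets, withdraws Day 8 | no event | event | failure |
| Stops Day 2, stays to Day 14 | event | event | failure |
| Stops Day 2, never answers again | unknown | unknown unless silence is a withdrawal | unknown unless silence is a withdrawal |

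The second row is the error: the Day 5 report already shows that the course was completed. The fourth row is the gap: no rule specific to this endpoint covers it.

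**Inputs for the size**
- N = 750 per arm and L = 0.20 lost (Protocol 11.2).
- d = true stopping by Day 5: 5% placebo, 10% drug. Assumed; not in the documents.
- u = share of the lost who leave after Day 5: 0.5. Assumed.
- w = share of the lost who formally withdraw: unknown, varied from 0 to 1.
- Loss is equal in both arms and unrelated to stopping. Assumed.
- Silent before Day 5 is scored as a non-event (inferred from the SAP Clarifications). Silent after Day 5 has a known Day 5 status.

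**Formulas**
- Failure proportion as written: p = (1 − L)d + Lw + L(1 − w)ud
- With a cut-off at the last dose: p* = (1 − L)d + Lud + L(1 − u)w
- Completers scored as failures: N × (p − p*) = N × L × w × u × (1 − d)

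**Worked case, all lost participants withdraw formally (w = 1)**
- As written, placebo: 0.8 × 0.05 + 0.2 = 0.24. Drug: 0.8 × 0.10 + 0.2 = 0.28. Risk ratio 0.28/0.24 = 1.17.
- With the cut-off, placebo: 0.04 + 0.005 + 0.10 = 0.145. Drug: 0.08 + 0.01 + 0.10 = 0.19. Risk ratio 0.19/0.145 = 1.31.
- Misclassified on placebo: 750 × 0.2 × 1 × 0.5 × 0.95 = 71.25, about 71.

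| w | As written, placebo vs drug | Risk ratio | With cut-off, placebo vs drug | Risk ratio | Placebo completers scored as failures |
|---|---|---|---|---|---|
| 0 | 4.5% vs 9.0% | 2.0 | 4.5% vs 9.0% | 2.0 | 0 |
| 0.5 | 14.25% vs 18.5% | 1.30 | 9.5% vs 14.0% | 1.47 | about 36 |
| 1 | 24% vs 28% | 1.17 | 14.5% vs 19.0% | 1.31 | about 71 |

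The cut-off does not restore the ratio of 2.0 when w is above 0, because withdrawals before the last dose still count as failures. The missing cut-off accounts for the step from 1.31 to 1.17 at w = 1, and from 1.47 to 1.30 at w = 0.5.

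**Sensitivity to the assumptions.** If 9/14 of the loss falls after Day 5, the upper count is 750 × 0.2 × (9/14) × 0.95, about 92. With true stopping of 10% and 20%, the ratio as written at w = 1 is 0.36/0.28 = 1.29.

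**Do the SAP sensitivity analyses repair this?** Not for late withdrawals. Both act on missing outcomes. A late withdrawer has been assigned a value, failure, so neither analysis changes that score.

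**The case against.** Section 3.2.2 openly names withdrawal as part of the endpoint, so it can be defended as a declared composite of stopping or leaving. That stands for 3.2.2 alone. The Summary omits withdrawal, and 5.3.3 names completion of medication, which a Day 8 withdrawal does not undo. One could also read 5.3.3 as meaning only withdrawals during dosing. That is sensible, but the text does not say it.

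The SAP sensitivity analyses are a fair answer to part of the problem. If the denominator rule applies here, so do they, and together they give the result among responders and both extremes for missing Day 5 reports. What they leave untouched is the late withdrawer.

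It is also fair that this is not the only information on tolerability. Section 3.2.2 lists adverse reactions separately, side effects are queried on Days 1, 3, 5 and 14, and the documents never call this endpoint a tolerability measure.

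A reader might go further and infer that the SAP scores silent non-responders as non-events, so that the endpoint measures follow-up loss. The documents do not support this. The clarification names no endpoint, and non-event status is only inferred from the alternatives listed beside it. Section 11.4 discusses loss to follow-up under a heading about withdrawn subjects, so silence and withdrawal are not cleanly separated. And if silent loss did add no events, the endpoint would reflect stopping plus formal withdrawal, not loss in general.

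A reader might also infer a 20-point swing. With an assumed 10% stopping among 600 responders, (60 + 150)/750 = 28% if all 150 lost withdraw formally, against 60/750 = 8% if all are silent. That contrast mixes two periods. The 8% needs all 150 to lack a Day 5 report, whereas the misclassification needs people who leave after it. If all 150 withdrew before the last dose, a cut-off would also give 28%. If all 150 withdrew after Day 5, the figures would be (75 + 135)/750 = 28% against a true 75/750 = 10%. That is an extreme case, and the 20% is a sample-size allowance for loss, not a withdrawal rate.

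**Conclusion.** The point holds in limited form. As written, 5.3.3 misclassifies participants who complete the course and withdraw on Days 6 to 14; the endpoint has three non-equivalent wordings; and no rule specific to it covers a missing Day 5 report.

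The size cannot be fixed from the documents, because they do not say how many lost participants will withdraw formally or when. Under the stated assumptions, between 0 and about 71 of 750 placebo participants are misclassified, and the risk ratio of 2.0 is seen as 2.0 (none withdraw formally) down to about 1.17 (all do). Part of that dilution comes from withdrawals during dosing and would remain with a cut-off. The effect shown is dilution. A spurious difference between arms would need unequal withdrawal, for which the documents give no figure.

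This is a minor point on a secondary endpoint. It does not touch the primary analysis of either cohort.

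**What to change.** Define the endpoint once, in the same words in the Summary, 3.2.2, 5.3.3 and the SAP: stopping study medicine before the last scheduled dose, classified from the Day 5 report. Then:
- count a withdrawal as a failure only if it precedes that dose;
- report later withdrawal, and missing Day 5 status, separately by arm;
- state in the SAP how a missing Day 5 report is scored for this endpoint, and that the existing exclude-missing and missing-as-event analyses apply to it;
- say what applies if the Day 5 survey is answered before the last dose, since section 7 allows for later delivery after weekend enrollment.

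The cost is a small amount of wording and programming. No new data are needed, provided that the Day 5 form shows whether the full course was taken. The documents show only that adherence is collected that day and that the SAP splits it at 75%.
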